#### **Morphine consumption [number]**

The number of morphine preparations taken per day is counted and documented.

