----------------------------------	---

Objective(s):	
In this study, the effect of repeated cold application with dynamic compression with the Game Ready and a control group will be investigated. The influence of these interventions and their effects will be investigated after a total knee endoprosthesis operation has been performed during the hospital stay. The change in the following parameters is examined: questionnaire on everyday activity and patient satisfaction, joint circumference in mm, skin temperature in C°, range of motion in degrees, morphine consumption in number per day, Pain sensation with the VAS, the length of the days of stay, the 10-meter walking test and the timed up-and-go in seconds.
 
The aim is to determine the effects of cold application with dynamic compression in order to be able to make recommendations. The current scientific knowledge requires further studies to substantiate or refute effects that have already been established.

Outcome(s):	
Primary outcomes
 
 
-Questionnaire Everyday Activity [Score]
 
-Patient satisfaction [cm]
 
-Joint circumference [mm]
 
-Range of motion [degrees]
 
-Skin temperature [°C]
 
-Morphine consumption [number]
 
- Visual analog pain scale [cm]
 
-Duration of stay [days]
 
-10-meter walk test[s]
 
-Timed-Up-and-Go [s]
 

Design:	Randomized, controlled trial

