
Visit 1: Screening and baseline preoperatively: information, written consent, examination of /Exclusion criteria, health questionnaire
 
Physical Function [Score]
 
Joint circumference [mm]
 
Range of motion [degrees]
 
Skin temperature [°C]
 
Visual Analog Pain Scale [cm]
 
10-meter walk test [sec]
 
Timed-up-and-Go [sec]
	60 min

Daily cooling intervention
 
In addition to the usual physiotherapeutic treatment: Daily Cooling and compression. One detailed treatment description can be found in chap. 8.1.1.
	
2x daily one treatment of 60 min = 120 min per day
 
4x 120 min per day = 480 min per stay

Visit 2: Follow up 4th postoperative day
 
Physical Function [Score]
 
Joint circumference [mm]
 
Range of motion [degrees]
 
Skin temperature [°C]
 
Visual Analog Pain Scale [cm]
 
Patient satisfaction [cm]
 
10-meter walk test [sec]
 
Timed-up-and-Go [sec]
	30 min

Visit 3: Follow up 6 weeks postoperatively  Physical Function [Score] Joint circumference [mm] Range of motion [degrees] Skin temperature [°C] Visual Analog Pain Scale [cm] 10-meter walk test [sec] Timed-up-and-Go [sec] Length of stay [days] Morphine consumption [number]	40 min
Total time commitment:	610 min

Any adverse events must be recorded during each visit. These possible time expenditures are not included in the test protocol.

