#### **Length of stay [days]**

The number of hospitalisation days (from admission to and with discharge) is counted and documented.

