#### Morphine consumption [number]

H0: The intake of morphine is not reduced by cryotherapy with intermittent dynamic compression compared to control groups during hospitalization.

H1: The intake of morphine is reduced by cryotherapy with intermittent dynamic compression compared to the control group during a hospital stay.

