#### Length of stay [days]

H0: The length of stay in hospital is not shortened by cryotherapy with intermittent dynamic compression compared to control groups during a hospital stay. H1: The length of stay in hospital is shortened by cryotherapy with intermittent dynamic compression compared to control groups during a hospital stay.

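### Morphine has no fixed counting window and no stated summary, so its result can depend on length of stay, which is itself a hypothesised treatment effect

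*Combined protocol and SAP*

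**What the plan says.** Sections 5.1 and 9.2.1 define the measure in one sentence: "The number of morphine preparations taken per day is counted and documented". The unit varies. The synopsis objective has "morphine consumption in number per day", while the outcome lists in the synopsis and in sections 4.1 and 4.2 give a plain number.

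The alternative hypothesis in section 11.1 is: "The intake of morphine is reduced by cryotherapy with intermittent dynamic compression compared to the control group during a hospital stay". It gives no first day, last day or number of days.

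Length of stay is on the same primary list. Section 9.2.1 defines it thus: "The number of hospitalisation days (from admission to and with discharge) is counted and documented". Its hypothesis in section 11.1 reads: "The length of stay in hospital is shortened by cryotherapy with intermittent dynamic compression compared to control groups during a hospital stay". Section 3.4 cites two earlier studies that reported shorter stays.

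In the test log (section 9.1) morphine does not appear at baseline or at the Day-4 visit. It appears once, at the 6-week visit, beside length of stay: "Length of stay [days] Morphine consumption [number]". The primary analysis (section 11.4.2) is a repeated-measures model with time levels at baseline, Day 4 and 6 weeks. It has no daily level. The opening of section 5.1 names the 4th postoperative day as the primary endpoint.

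**The concern.** Daily counts have no place in a model with three time levels until a rule says which count, or which combination of counts, enters it. The plan gives no such rule. The only period attached to the morphine hypothesis is the hospital stay, and the plan expects treatment to change how long that lasts.

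A mean per hospital day and a total over the stay are both natural readings of the two units in the text. Each can carry discharge timing into the morphine result. If use falls after surgery, a shorter stay keeps mainly the heavy early days and raises the mean. It also drops later days, which lowers the total or leaves it unchanged. A device that only brought discharge forward could then seem to worsen or improve morphine use, depending on the summary. Section 11.4.2 places the analysis after data collection is complete, so the summary would be chosen once the data exist.

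**Working it through.** There is no figure in the plan to reproduce: it gives no morphine mean, no SD and no expected length of stay. The check is therefore whether identical use can give different scores under the summaries that the text allows. All counts and stays below are assumed.

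**Formulas.** For daily counts c1, c2, … and a stay of L days: stay total = c1 + … + cL; stay mean = stay total / L; fixed-window total = c1 + … + c4, taking a four-day window for illustration.

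**Declining course 6, 5, 4, 3, 2, 1, 0, the same in both patients**
- 5-day stay: total 6+5+4+3+2 = 20; mean 20/5 = 4.0.
- 7-day stay: total 6+5+4+3+2+1+0 = 21; mean 21/7 = 3.0.
- Fixed window: 6+5+4+3 = 18 in both.

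**Constant 2 per day, the same in both patients**
- 5-day stay: total 10; mean 2.0.
- 7-day stay: total 14; mean 2.0.
- Fixed window: 8 in both.

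| Assumed course | Summary | 5-day stay | 7-day stay | Shorter stay relative to longer |
|---|---|---|---|---|
| Declining | Stay mean | 4.0 | 3.0 | 4.0/3.0 − 1 = +33% |
| Declining | Stay total | 20 | 21 | 20/21 − 1 = −5% |
| Declining | Four-day total | 18 | 18 | 0% |
| Constant | Stay mean | 2.0 | 2.0 | 0% |
| Constant | Stay total | 10 | 14 | 10/14 − 1 = −29% |
| Constant | Four-day total | 8 | 8 | 0% |

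**Second declining course, 6, 4, 3, 2, 1, 1, 0, 0.** For stays of 4, 5, 6, 7 and 8 days the stay means are 3.75, 3.20, 2.83, 2.43 and 2.12. The stay totals are 15, 16, 17, 17 and 17. The four-day total is 15 throughout. The pattern is the same: earlier discharge raises the mean and lowers the total or leaves it level.

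Whether a distortion arises, and in which direction, depends on the course of use and on the summary. The fixed-window total does not depend on stay as long as every patient is observed to the end of the window.

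**The case against.** The plan never says that morphine is averaged or summed over the stay. The hospital-stay phrase in the morphine hypothesis is also stock wording. The hypotheses for joint circumference, skin temperature, pain, walking time and timed-up-and-go use it too, and those outcomes are measured at fixed visits. Section 5.1 makes Day 4 the primary endpoint for the parameters listed under it, and morphine is among them. Comparing the count on Day 4 alone would fit that text and has no stay denominator for patients still in hospital. Section 6.2.2 also blinds the statistician, which limits a choice of summary made to favour one arm.

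Much of this stands. A reader might infer that the plan scores morphine as a mean over the stay, so that identical use always gives different scores when stays differ. The documents do not support that. No section divides by length of stay, and at constant daily use a stay mean does not move at all. Nor do they support saying that the two outcomes are coupled whichever summary is used, or that counting certainly runs to discharge.

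The objection does not supply the missing definition. The Day-4 visit in the test log has no morphine entry, and the single entry is at 6 weeks beside length of stay. The Day-4 reading is therefore possible but not chosen. Blinding the statistician does not stop a stay-based summary from carrying discharge timing.

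**Conclusion.** The point holds as one about an undefined window and summary. The plan leaves open a morphine score that depends on length of stay, and length of stay is a hypothesised treatment effect. On the assumed 5- and 7-day stays, the shorter stay scores between 0% and 33% higher on a stay mean, and about 5% to 29% lower on a stay total. These figures rest entirely on assumed counts and stays. The size of any bias in this trial, and its direction, cannot be derived from the documents. One of the ten listed primary outcomes is affected, and the gap should be closed before the data are analysed.

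**What to change.** In sections 5.1, 9.2.1 and 11.1, define the morphine outcome as the total number of preparations over one fixed postoperative window, identical for every patient. State:

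- the start, for example the end of surgery;
- the end, at the Day-4 assessment that section 5.1 already names as the primary endpoint;
- how a patient discharged before the window ends is handled. Either use is recorded up to the end of the window, or the count is treated as missing under a stated rule. Dropping such patients under the complete-data rule in section 11.4.1 would select on discharge timing again.

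In section 11.4.2, say that this single total is compared between the groups, since it has no baseline or 6-week level. Align the test log with the new definition. Report later in-hospital use descriptively.

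The cost is mainly wording, because daily counts are already documented. Any recording after early discharge would be extra work. The price is that use after Day 4 leaves the primary score.

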In addition to standard physiotherapy (see Chapter 8.1.2 for more information), the subjects in the intervention group will receive the following intervention (according to the manufacturer's protocol for patients with total knee endoprosthesis): 48 hours after the operation, the intervention starts, if tolerable, with little compression (level 1 = 5-15 mmHg) and cooling at the coldest level tolerable by the participant (corresponds to program 2). The cooling should be perceived as "pleasant" by the participant. The intervention lasts one hour, of which 30 minutes are on and 30 minutes off cycles. The on cycle includes the duration of the intervention (cooling and compression), while the off cycles include the rest period. After 60 minutes, the device is removed. If compression is not tolerated, it can also be omitted on the first postoperative day (corresponds to program 1). The intervention is performed twice a day for the first four days after surgery. The coldest tolerable temperature level is to be determined anew for each treatment. The compression level may be increased, although medium compression may only be applied from the second day onwards (corresponds to program 3).

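### Morphine consumption, a primary outcome, is a daily count of preparations with no dose, and neither the days counted nor the summary of the daily counts is defined.

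*Combined protocol and SAP*

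**What the plan says.** The synopsis and section 4.2 list morphine consumption among ten primary outcomes, with the unit given only as a number. Sections 5.1 and 9.2.1 carry the same one-sentence definition: "The number of morphine preparations taken per day is counted and documented". The alternative hypothesis in 11.1 is: "The intake of morphine is reduced by cryotherapy with intermittent dynamic compression compared to the control group during a hospital stay".

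Length of stay is defined separately: "The number of hospitalisation days (from admission to and with discharge) is counted and documented". In the test log (9.1) morphine appears once, at the 6-week visit beside length of stay. The primary analysis (11.4.2) crosses group with a three-level time factor: baseline, day 4 and 6 weeks.

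On device timing, 8.1.1 contains three statements:
- "48 hours after the operation, the intervention starts, if tolerable"
- "The intervention is performed twice a day for the first four days after surgery"
- if compression is not tolerated, "it can also be omitted on the first postoperative day"

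The test log budgets four days of 120 min, 480 min per stay.

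**The concern.** There are two gaps.

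**Dose.** The hypothesis is about how much morphine is taken, but the variable is how many preparations are taken. If more than one strength or opioid is in use, the two can disagree, and the mismatch adds noise to the group comparison.

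**Window and summary.** The definition gives no first day, no last day, and no rule for turning daily counts into the value that is tested. The hypothesis points to the hospital stay. Part of that stay precedes any device use, and the device cannot affect morphine taken then. If daily counts are totalled over the stay, the total also depends on length of stay, which is itself a listed outcome.

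At stake is the sensitivity of one primary outcome in a trial of 14 per arm. In addition, the window and summary could be chosen after the data have been seen.

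**Working it through.** **1. The plan's own figure.** No calculation is specific to morphine. The only figure is 28 subjects (14 per group), with power 0.95 and a 5% level in 11.2 and an effect size of 0.8 in the synopsis. Read as a standardised mean difference in a two-sided two-sample t test, 14 per arm gives power 0.53, and power 0.95 needs 42 per arm. So 28 is not reproduced on that reading. Figure 4 is not shown, so the test family is unknown. That is a separate matter. Here 0.53 is only the reference value for step 4.

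**2. Count against dose.** Take assumed strengths of 5 and 20 mg. Two 5 mg preparations score 2 and deliver 2 × 5 = 10 mg. One 20 mg preparation scores 1 and delivers 20 mg. The ranking by count reverses the ranking by intake.

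**3. Power lost by counting (illustration).** Assumptions: log-normal daily dose, median 60 mg, log-SD 0.5, true reduction 0.8 SD (0.8 × 0.5 = 0.4 on the log scale), 14 per arm, Mann-Whitney test at 0.05, 2000 simulated trials per scenario, strength unrelated to arm. Power on milligrams was 0.48 to 0.52 across runs.

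| Strengths in use (assumed) | Strength varies dose by dose | Each patient keeps one strength |
|---|---|---|
| 5 and 10 mg | 0.46 | 0.34 |
| 10 and 20 mg | 0.45 | 0.35 |
| 5, 10 and 20 mg | 0.41 | 0.23 |
| One strength only | no loss | no loss |

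Repeat runs moved the last column by up to about 0.03.

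**4. Dilution if days are pooled (illustration).** Let the stay total be 2 untreated days plus h treated days, with a 0.8 SD effect on the treated part only. Assume equal daily SDs, period SD proportional to days, and correlation ρ between the two periods. Then

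d = 0.8h / √(h² + 2² + 2ρ·2·h).

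- h = 2, ρ = 0.9: 1.6 / √(4 + 4 + 7.2) = 0.41, power 0.18.
- h = 2, ρ = 0: 1.6 / √8 = 0.57, power 0.30.
- h = 5, ρ = 0: 4 / √29 = 0.74, power 0.47.

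Over h = 2 to 5 and ρ = 0 to 0.9, d is 0.41 to 0.74 and power 0.18 to 0.47, against 0.53 if only treated days are used. If the daily SD is twice as large in the first 48 h, d is 0.27 to 0.62 and power 0.11 to 0.36.

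**5. How long is the untreated time?** With counting from surgery and a 48 h start, the untreated share is 2 of 4 days (50%) or 2 of 7 days (29%); both lengths are assumptions. The 48 h start is not settled, however. Starting at 48 h and stopping after the fourth postoperative day leaves about 4 − 2 = 2 treatment days, or 2 × 120 = 240 min, against the 480 min budgeted. The provision for the first postoperative day also implies treatment before 48 h. Because the stay runs from admission, some of it precedes the device on every reading. Only the length is uncertain.

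**6. Fit with the planned analysis.** Baseline, day 4 and 6 weeks are measurement visits. None defines an in-hospital morphine window, so 11.4.2 does not say what value of this outcome enters the model.

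**The case against.** A reader might infer that the plan scores morphine over a period that includes 48 untreated hours. The documents do not say so. The definition is per day, so treated and untreated days could be separated, and pooling over the stay is neither stated nor excluded. The 48 h start also conflicts with other wording in 8.1.1 and with the 480 min. What stands is that the window and summary are undefined, and that the hospital-stay wording does not exclude time before the device.

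A reader might also take the effect to be halved to 0.4 SD. That needs equal treated and untreated time and near-perfect correlation between them. Likewise, the larger power losses on counts arise only if each patient keeps one randomly assigned strength. When strengths vary within patients, the loss is roughly 5 to 10 points.

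Two further points carry weight. This is a single hospital, and if one strength is standard there, the dose problem costs nothing. And 12.2.1 says morphine is noted on the data collection form, an appendix that is not available and may record dose. Neither removes the gap in the plan: the text requires no single strength and states no dose-based outcome.

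Finally, with randomised arms both problems mainly add noise or dilute. Directional bias would need preparation choice to differ by arm. That is possible, since participants are not blinded (6.2.2), but nothing in the documents shows it.

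**Conclusion.** The point holds in two parts. First, as written, the outcome does not measure intake of morphine if strengths or opioids differ, because the available text has no dose. Second, its window and summary are undefined, the natural reading includes some time before the device starts, and the planned time factor does not fit it.

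The size is illustrative only. The loss from counting runs from none (single strength) to more than half of the power (several strengths, one kept by each patient). The loss from pooling depends on the assumed number of treated days and on the correlation. Strengths, dose distribution, stay length and correlations are all assumptions, since the documents give none of them. The consequence is limited to one of ten primary outcomes.

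**What to change.** 1. Record drug and dose from the medication chart. Define the outcome as total morphine-equivalent milligrams per 24 h, using one conversion table fixed in advance. Keep the count as descriptive. If the data collection form already captures dose, say so in 5.1 and 9.2.1.
2. Reconcile the passages on device timing: 48 hours after surgery, the first four days after surgery, the first postoperative day, and 480 min.
3. Then state the window. It should run from the reconciled planned start of device treatment to a stated end, with the same postoperative window in controls. Adjust only for use before that start. A window and covariate fixed at 48 h before the passages are reconciled could put treated time into the covariate or drop treated time from the outcome.
4. Name the summary and the test for this outcome, since the three-visit model does not supply them.

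The cost is slightly more data entry, one conversion table and a few sentences of text. No treatment changes.

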#### **Visual Analog Pain Scale [cm]**

The Visual Analog Pain Scale is documented at rest. The scale is scaled from 0 (no pain) to 10 (greatest pain imaginable) in cm increments. The test subjects are asked the following question: "How severe is your knee pain?" The measurement moments take place preoperatively, on the 4th postoperative day and 6 weeks postoperatively.

#### **10-meter walk test [sec]**

The 10-meter walking test is used because it is considered a valid and reliable measuring instrument for evaluating walking speed (Peters, Fritz, and Krotish 2013). In this assessment, the subject is asked to walk a distance of 10 meters as quickly and safely as possible. The examiner documents the time in seconds. The measurement moments take place preoperatively, on the 4th postoperative day and 6 weeks postoperatively.

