## 5. CLINICAL INVESTIGATION OUTCOMES

### 5.1 Primary Outcome

This study aims to investigate the effects of cryotherapy with intermittent dynamic compression with Game Ready during a hospital stay. The preoperative measurement is the baseline, the 4th postoperative day is the primary endpoint and the measurement 6 weeks postoperative is declared as follow-up. The following parameters are examined for this purpose:

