#### **10-meter walk test [sec]**

The 10-meter walking test is used because it is considered a valid and reliable measuring instrument for evaluating walking speed (Peters, Fritz, and Krotish 2013). In this assessment, the subject is asked to walk a distance of 10 meters as quickly and safely as possible. The examiner documents the time in seconds. The measurement moments take place preoperatively, on 4 weeks postoperative day and 6 weeks postoperatively.

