## 5.4 Safety Outcomes

No further outcomes are included that serve safety. Discontinuation of the experiment is the responsibility of the examiners with regard to the subject's resilience. If this is estimated to be too low, the examiner can stop the experiment. If the subject does not feel well according to his or her own subjective assessment, he or she can discontinue the experiment and withdraw participation in the study. If the cold application is not justifiable for the test subject, he or she can discontinue the application. There are no disadvantages for him/her as a result. The current regulations of the Canton of Graubünden and those of the FOPH for protection against the coronavirus will be taken into account and implemented when conducting the study.

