#### **Timed-Up-and-Go [sec]**

The time-up-and-go is used because it is considered a valid and reliable measuring instrument for the evaluation of physical activity after hip and knee prostheses (Dobson et al. 2012). The subject is asked to rise from a chair while sitting and walk three meters, turn around and sit down again. The time spent on this task is measured in seconds. The measurement moments take place preoperatively, on the 4th postoperative day and 6 weeks postoperatively.

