## 11.4 Planned Analyses

### 11.4.1 Datasets to be analysed, analysis populations

Only complete data sets will be included in the study. Data that contains only part of the protocol is not included in the analysis. No new subjects are being sought to replace the missing data.

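### The 10-metre walk and Timed-Up-and-Go have no value for a patient who cannot do them on Day 4, so the complete-data rule removes patients because of a bad outcome

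*Combined protocol and SAP*

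**What the plan says.** Section 5.1 states that "the 4th postoperative day is the primary endpoint". Section 9.2.1 schedules the 10-metre walk as follows: "The measurement moments take place preoperatively, on the 4th postoperative day and 6 weeks postoperatively". The visit tables in 9.1 list the walk and the Timed-Up-and-Go on that day. (The walk paragraph in 5.1 speaks of weeks where 9.2.1 and 9.1 give the fourth day; these need to be reconciled.)

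The walk is described in one instruction: "In this assessment, the subject is asked to walk a distance of 10 meters as quickly and safely as possible". Each test yields one number. For the walk, "The examiner documents the time in seconds"; for the Timed-Up-and-Go, "The time spent on this task is measured in seconds". Neither 5.1 nor 9.2.1 gives a code, a time limit or a worst value for a patient who cannot finish.

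The analysis set is defined per subject. Section 11.3 admits only subjects who went through the whole protocol. Section 11.4.1 adds: "Data that contains only part of the protocol is not included in the analysis", and seeks no replacements for missing data. Section 11.5 keeps non-completers' data but leaves them out of the final analysis. No imputation or sensitivity analysis is planned.

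**The concern.** A patient who cannot walk the 10 metres four days after knee replacement has no time in seconds. The blank is not an accident of data collection: it is the worst possible result on that outcome. Under the rules in section 11 it removes the patient, including that patient's KOOS, pain, circumference, range of motion, skin temperature, morphine count and length of stay.

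If the device helps early mobility, more controls than device patients will be unable. The worst controls then leave the comparison and the measured benefit shrinks. If the device delays mobility, harm is hidden in the same way. In both cases the walking results describe only patients fit enough to be timed.

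This differs from the general objection to complete-case analysis. If the rule were applied outcome by outcome, the other measures would be kept, but the two walking tests would still lose these patients, because seconds have no value for inability.

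**Working it through.** The plan states no inability rate and no related figure, so there is nothing of its own to reproduce here. What follows are scenarios.

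**Inputs from the documents**
- 14 patients per group, 28 in total (section 6.1).
- Effect size 0.8 (synopsis). The text does not say whether this is d or f; it is read here as d, a difference in SD units.

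**Assumptions**
- Latent Day 4 mobility is normal with SD 1 in each group.
- One ability threshold applies to both groups.
- The share p of controls unable is 5%, 10%, 20% or 30%.

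**Formulas**
- Threshold: z = Φ⁻¹(p).
- Share unable on device: p₁ = Φ(z − d).
- Upward shift of the mean among testable patients: λ₀ = φ(z)/(1 − p) for control, λ₁ = φ(z − d)/(1 − p₁) for device.
- Difference among testable patients: D = d + λ₁ − λ₀.
- Variance among testable patients: 1 + zλ₀ − λ₀² for control, and 1 + (z − d)λ₁ − λ₁² for device.

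**Worked case, p = 20%**
- z = −0.842 and p₁ = Φ(−1.642) = 5.0%.
- λ₀ = 0.350 and λ₁ = 0.109, so D = 0.8 + 0.109 − 0.350 = 0.559.
- The SDs among testable patients are 0.764 and 0.899. The root mean variance is 0.834, so the standardised difference is 0.559/0.834 = 0.67.

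| Controls unable | Device unable | Expected n, control/device | D in original SD (loss) | D standardised to truncated SD (loss) |
|---|---|---|---|---|
| 5% | 0.7% | 13.3/13.9 | 0.71 (11%) | 0.76 (5%) |
| 10% | 1.9% | 12.6/13.7 | 0.65 (19%) | 0.73 (9%) |
| 20% | 5.0% | 11.2/13.3 | 0.56 (30%) | 0.67 (16%) |
| 30% | 9.3% | 9.8/12.7 | 0.49 (39%) | 0.62 (22%) |

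With a true difference of 0.5 SD, D in original units is 0.43, 0.39, 0.33 and 0.28.

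**Other outcomes.** For an outcome with a true difference of 0.8 SD and correlation r with mobility, the difference becomes 0.8 − r(0.8 − D). At 20% of controls unable:
- r = 0: 0.80, no loss.
- r = 0.3: 0.8 − 0.3 × 0.241 = 0.73.
- r = 0.5: 0.8 − 0.5 × 0.241 = 0.68.

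**Chance of losing anyone.** If a share q of all 28 patients is unable, the chance of at least one loss is 1 − (1 − q)²⁸. This is 76% at q = 5% and 95% at q = 10%.

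**Effect of scoring inability.** In a simulation of 20,000 trials under the same model (two-sided 5% tests of the Day 4 difference), the complete-case t-test has power 0.48, 0.43, 0.35 and 0.28 across the four scenarios. A Mann-Whitney test on all 28 with unable as the worst rank stays at about 0.49. A t-test with nobody missing has about 0.53. These figures compare ways of handling inability. They do not test the plan's sample-size calculation, whose inputs are in a figure not shown.

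**The case against.** **Inability may be rare.** Section 8.1.2 has patients loading the operated leg from the first postoperative day as symptoms allow, and nothing in the test descriptions forbids arms or walking aids. No document supports a rate of 20% or 30%. At 5% the standardised loss is about 5%. This stands: the size is unknown and could be small. The rule is still open, because the same section makes loading depend on symptoms.

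**The data form might hold the missing code.** Section 12.2.1 says these results go on a data collection form, which is an appendix not shown. A reader might infer that inability and walking aids go unrecorded. The documents do not support that; they show only that the protocol body specifies neither. Even with a code on the form, section 11 would have to say how it is analysed.

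**Not every outcome shrinks alike.** A reader might infer that the benefit shrinks by the mobility percentages on all outcomes. It does not: the whole data set is lost, but the bias in another measure depends on its correlation with mobility and is zero when that is zero.

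**The stopping provision is not a rule about failed tests.** Section 5.4 says of the subject's resilience: "If this is estimated to be too low, the examiner can stop the experiment". It is tempting to read this as the examiner ending a walk test. It is a general provision, and a patient stopped under it is a drop-out, which is a different route.

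**Much of the damage comes from the complete-data rule.** That is true of the other outcomes, and repairing the rule would keep them. It would not give the two walking tests a value for inability.

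**Seconds and speed carry the same information.** For anyone who finishes, they do. Section 9.2.1 justifies the walk because "it is considered a valid and reliable measuring instrument for evaluating walking speed", and only on the speed scale does inability have a natural value, zero. Zeros do put a point mass into a repeated-measures ANOVA with 14 per group, which favours a rank test.

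**Conclusion.** The point holds in a limited form. As written, the protocol body gives the 10-metre walk and Timed-Up-and-Go no value for inability at the primary time point, and sections 11.3, 11.4.1 and 11.5 then exclude the patient. Exclusion therefore depends on the outcome being measured.

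The size is conditional. It rests on an assumed inability rate, normal latent mobility, a common threshold and the stated 0.8 read as d. Over 5% to 30% of controls unable, the mobility difference falls from 0.80 to between 0.71 and 0.49 in original SD units, or to between 0.76 and 0.62 standardised to the truncated SD. Other outcomes lose less. If nobody is unable, there is no effect. The plan should settle this before data are seen, since a score chosen afterwards is open to bias.

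**What to change.** 1. State in 9.2.1 that the blinded examiner records unable to complete when a patient cannot do either test.
2. State in 11.3 and 11.4.1 that this entry counts as a complete value, so the patient's other outcomes stay in the analysis.
3. Analyse Day 4 walk and Timed-Up-and-Go with unable as the worst rank (or the walk as speed, 10 divided by seconds, with 0 m/s for unable). Compare the groups with a rank test and report the number unable by arm.
4. Check that the data form has fields for unable and for the walking aid used, and add them if not.

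Cost: at most two form fields and one further analysis per test in SPSS, with no extra visits. The downside is that these two results are read as ranks or m/s instead of seconds, and that the rank test is an addition to the planned repeated-measures ANOVA and must be specified as such.
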